7 CONCURRENT MEDICATIONS

All subjects should be maintained on the same medications from screening through Visit 5 (Day 28), as medically feasible, with no introduction of new chronic therapies. Medication history will be collected for all drugs for the 30 days prior to screening. If any changes in concomitant medications are required due to AEs (i.e. illness, laboratory abnormalities, surgical procedures, etc.), the reason(s) for the change(s) must be documented. Subjects who require treatment for a pulmonary exacerbation during the course of the trial will remain in the study.

Subjects who have routinely taken more than 10 mg/day (or >20 mg on alternate days) of prednisone or other systemic corticosteroids 4 weeks prior to Visit 1 (Day -42 to -10) or who have taken these medications as needed within 72 hours prior to Visit 1 or 2 will be excluded from participation. Subjects may be re-screened once. For those subjects taking alternate month TOBI® or Cayston® therapy, on/off cycles must be timed such that a subject is at the same phase of a cycle at Visits 2, 3, 4, and 5.

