DOSE AND MODE OF ADMINISTRATION	dose escalation using the “3+3” design ¹ will be employed. The three doses are 1×10^6 , 3×10^6 , and 5×10^6 hMSCs/kg. Allogeneic MSCs will be derived from bone marrow aspirates from a healthy donor whose serum tests negative for cytomegalovirus (CMV) antibodies. Healthy donors will undergo tests for infectious disease and screening for 41 common CFTR mutations. In addition, the MSCs will be validated for in vitro and in vivo efficacy and potency using the in vivo murine pre-clinical model of CF lung infection and inflammation.
CONTROL PRODUCT, DOSE AND MODE OF ADMINISTRATION	NA
DURATION OF SUBJECT PARTICIPATION AND DURATION OF STUDY	Subjects will be studied for approximately 13 months Screening: between 10 and 42 days Treatment: 1 day Follow-up: 12 months We anticipate 15 months to recruit subjects (due to the 3+3 safety study design). The last subject in each cohort must finish Visit 5 before enrolling the first subject in the next cohort.
CONCOMITANT MEDICATIONS	For those on alternate month TOBI® or Cayston® therapy, on/off cycles must be timed such that a subject is at the same phase of a cycle at Visits 2-5. Allowed: All routine chronic CF medications. 
Prohibited: Anti-inflammatory medications (hydroxychloroquine, corticosteroids >10mg daily or >20 mg on alternate days) and immunosuppressants between Visits 1 and 5. Changes in chronic treatment of CF (e.g., introduction, dose escalation, or elimination of chronic therapies) between Visits 1 and 5.
SAFETY EVALUATIONS	Dose-limiting toxicities, adverse events, including pulmonary exacerbations; Cystic Fibrosis Respiratory Symptom Diary (CFRSD); Respiratory and Systemic Symptoms Questionnaire (RSSQ); physical examination; assessment of vital signs, including oxygen saturation; spirometry, sputum bacterial culture (quantitative and qualitative); hematology, comprehensive chemistry, erythrocyte sedimentation rate (ESR), high-sensitivity C-reactive protein (hs-CRP), and urinalysis

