5 CRITERIA FOR EVALUATION

5.1 Primary Endpoint

The primary outcome will be the safety and tolerability of a single infusion of allogeneic hMSCs. Study participants will be monitored for potential dose limiting toxicities. The dose limiting toxicity (DLT) definition consists of the emergence of infusion-related allergic AEs as well as regimen related toxicities. For this study, a DLT will be considered for the occurrence in the first 24 hours after hMSC infusion of a grade ≥ 3 infusion-related allergic toxicities, which include rash, flushing, urticaria, dyspnea, fever $>40^{\circ}\text{C}$ ($>104.0^{\circ}\text{F}$) as scored according to the National Cancer Institute (NCI) Common Terminology Criteria for Adverse Events (CTCAE) version 4.0. Finally, the CTCAE will be used to assess and grade AE severity, including laboratory abnormalities judged to be clinically significant. In addition to infusion related toxicities, special focus will also be placed upon detecting pulmonary exacerbations since anti-inflammatory therapies theoretically could suppress the immune system to the point where it leads to increased infectious complications. Appendix I lists the criteria for defining a pulmonary exacerbation treated with antibiotics. All AEs encountered during the study period will be captured and graded.

In addition to DLT, safety and tolerability of a single infusion of allogeneic mesenchymal stem cells will also be determined by

- Incidence and severity of AEs
- Number of pulmonary exacerbations (modified Fuch's definition⁹⁵)
- Diary reports (Cystic Fibrosis Respiratory Symptom Diary)
- Changes in subject reported symptoms as captured by the Respiratory and Systemic Symptoms Questionnaire from Baseline (Visit 2) Day 1 to Baseline (Visit 2) Day 2, Visits 3, 4, 5, 6, and 7 and at times when a pulmonary exacerbation is being considered.
- Changes in physical examination
- Changes in vital signs including oxygen saturation checked throughout the infusion

- Changes in spirometry (FEV₁ %, FEV₁ (Liters), FEF₂₅₋₇₅) determined 30 minutes, 4 hours and 24 hours after completion of infusion and from Baseline (Visit 2) Day 1 to Baseline (Visit 2) Day 2, Visits 3, 4, 5, 6 and 7.
- Change in sputum quantitative microbiology (change in bacterial colony forming units between Baseline Day 1 and Day 7 and Day 28)
- Changes in hematology, comprehensive chemistry, erythrocyte sedimentation rate (ESR), high-sensitivity C-reactive protein (hs-CRP), and urinalysis results

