9.1.8 Acquisition of Sputum

Sputum (approximately 1.3-2.0 grams) will be obtained at Visit 2 (Day 1) prior to the infusion of stem cells and on Visits 3 (Day 7) and 5 (Day 28) via spontaneous expectoration. Sputum samples will be split according to priority for analyses. The first aliquot will be sent to the microbiology laboratory at University Hospitals Cleveland Medical Center where quantitative bacteriology will be performed, and the second aliquot will be processed and saved for research studies. Sputum will be processed according to the current standard operating procedure (SOP) developed by CF Foundation's Therapeutics Development Network. Subjects unable to spontaneously expectorate sputum will undergo sputum induction according to the current SOP developed by CF Foundation's Therapeutics Development Network. If a sputum sample cannot be produced, or the quantity of the sample is not sufficient for all the tests to be performed, this is not considered a deviation.

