10.10 Visit 5 (Day 28 ± 2)

1. Review and record RSSQ prior to any other study procedures
2. Administer and review CFRSD prior to any other study procedures and record any AEs that occurred since Telephone call 2
3. Review and record interval history
4. Review and record any changes to concomitant medications
5. Measure and record weight without shoes
6. Perform and record vital signs, including a blood pressure after the subject has been seated for 5 minutes
7. Perform and record oximetry
8. Perform complete physical examination
9. Collect blood for clinical laboratory tests (comprehensive chemistry panel, ESR, hs-CRP, complete blood count with differential, direct bilirubin and LDH)
10. Collect blood for inflammatory mediators (calprotectin, MPO, GM-CSF, IL-1 β , IL-6, IL-8, IL-17, and TNF- α)
11. Collect urine for clinical laboratory test (urinalysis)
12. Collect urine for pregnancy test
13. Administer 3 puffs of albuterol 15 minutes prior to spirometry if subject is likely to require induction to obtain sputum during the visit
14. Perform and record spirometry
15. Obtain sputum for clinical laboratory tests (quantitative culture and microbiology) and for research tests (cell count with differential, IL-1 β , IL-6, IL-8, IL-10, IL-17, GM-CSF, MIP-3 α , TNF- α , neutrophil elastase, α_1 -anti-trypsin, and MMP-9). Subjects will be asked to provide sputum via spontaneous expectoration. If a subject is unable to provide sputum spontaneously, then the subject may undergo sputum induction according to the current TDN SOP. Any AEs related to the sputum procedure will be recorded
16. Schedule subject for **Telephone Call 3** and for **Visit 6**
17. Record any AEs that may have occurred during the study visit

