15.2 Demographic and Baseline Characteristics

Demographic and baseline clinical characteristics including age, gender, race, CFTR genotype, height, weight, oxygen saturation, sputum microbiology (presence of *P. aeruginosa*, methicillin-sensitive *S. aureus*, methicillin-resistant *S. aureus*, and/other Gram-negative bacteria) and pulmonary function will be reported for each subject and summarized overall using descriptive statistics such as frequency, percentage, mean or median and range. For all analyses, Baseline will be defined as the measurement prior and closest to the administration of the infusion of hMSCs.

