15.4 Analysis of Secondary/Exploratory Endpoints

Although efficacy is not the primary aim of this dose escalation study, changes and patterns of change between MTD and lower doses on inflammatory biomarkers in blood and sputum measured at Baseline, day 7 and day 28 will be explored using a mixed effects model, mean and standard deviation at each time point as well as each patient's case profile will be graphically presented.

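### The same-phase rule for alternate-month inhaled antibiotics puts Baseline within days of an on/off switch, so change in CFU and sputum markers can include the antibiotic's own effect, and the analysis does not separate it

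*Combined protocol and SAP*

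**What the plan says.** Section 7 applies a timing rule to subjects on alternate-month TOBI or Cayston: "on/off cycles must be timed such that a subject is at the same phase of a cycle at Visits 2, 3, 4, and 5". The synopsis repeats it. Neither place says whether the shared phase is to be on or off, how many days a phase lasts, or how far into a phase Day 1 should fall. Section 7.1 allows both drugs as ongoing chronic treatment.

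Visit 2 is Day 1, and section 10.10 lets Visit 5 fall from Day 26 to Day 30. Sputum is collected on Day 1 before the infusion, on Day 7 and on Day 28 (section 9.1.8). Section 15.2 states that "Baseline will be defined as the measurement prior and closest to the administration of the infusion of hMSCs", so Baseline is a single Day 1 value and not an average over a cycle.

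Section 5.1 includes among the safety measures "change in bacterial colony forming units between Baseline Day 1 and Day 7 and Day 28". Section 5.2 makes the sputum inflammatory markers secondary, over the same interval. Section 8.1 confirms that there is no placebo group. Under section 15.3 the CFU results are presented graphically. Under section 15.4 the biomarker patterns at the MTD and at lower doses "will be explored using a mixed effects model". Neither section mentions antibiotic phase as a covariate, a subgroup or a sensitivity analysis.

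**The concern.** The rule is evidently meant to keep antibiotic phase constant across the sputum comparisons. But the span from Day 1 to Visit 5 is almost as long as one phase. The only way to fit all four visits into one phase is to begin close to its start. Baseline then follows about a month of the opposite phase, while Day 7 and Day 28 lie progressively deeper in the current one. The antibiotic switch and the infusion happen at nearly the same time.

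Without a control arm, the change within a subject cannot tell the two apart. A subject starting an on-phase could show falls in CFU and markers that resemble the hoped-for effect of the cells. A subject starting an off-phase could show rises that resemble the infectious harm the protocol says it is watching for. In cohorts of three, a chance difference in the number of on-phase and off-phase starters could also distort the comparison of dose levels.

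**Working it through.** The plan states no figure on this point, so there is none to reproduce. The check is calendar arithmetic, followed by an illustration of size.

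**Step 1: where Day 1 can fall.** Let a phase last L days, let Day 1 be phase day k, and let Visit 5 be on Day v. Visit 5 then falls on phase day k + v − 1. The rule needs k + v − 1 ≤ L, so k ≤ L − v + 1. The values of v come from section 10.10. L = 28 to 31 is an assumption drawn from the term alternate month.

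| Phase length L | Visit 5 on Day 26 | Visit 5 on Day 28 | Visit 5 on Day 30 |
|---|---|---|---|
| 28 | k = 1–3 | k = 1 | none |
| 29 | k = 1–4 | k = 1–2 | none |
| 30 | k = 1–5 | k = 1–3 | k = 1 |
| 31 | k = 1–6 | k = 1–4 | k = 1–2 |

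Day 1 is therefore always phase day 1 to 6. Day 7 falls on phase day 7 to 12 and Visit 5 on phase day 26 to 31. For a 28- or 29-day phase, a Day 30 visit is inside the window of section 10.10 but cannot satisfy section 7.

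*Same phase* cannot mean the same point in the cycle. That point next recurs on Day 1 + 2L, which is Day 57 (L = 28) to Day 63 (L = 31), well after Visit 5.

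**Step 2: how much of the on/off effect enters the change from Baseline.** As an illustration only, suppose the measure moves exponentially towards the level of the new phase with a half-life of 1, 3 or 7 days (assumed), after repeated on/off cycling.

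| Start | Share of full effect at Day 7 | Share of full effect at Day 28 |
|---|---|---|
| L = 28, Day 1 on phase day 1 | 42–98% | 88–100% |
| L = 31, Day 1 on phase day 4 | 12–37% | 12–66% |

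With Day 1 on phase day 1, the share rises as the half-life shortens. With Day 1 on phase day 4, a fast-acting antibiotic has done most of its work before Baseline, so at Day 28 the smallest share (12%) belongs to the shortest half-life.

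**Step 3: effect on a mean.** Let E be the on/off effect in log10 CFU, assumed to be 0.5 to 2 because the documents give none. In a group of n with m_on on-phase starters and m_off off-phase starters, a fully expressed effect shifts the mean by (m_off − m_on) × E / n.

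- One user in a cohort of three: 0.5/3 = 0.17 to 2/3 = 0.67 log10, down or up according to phase.
- The same subject with only 12–66% of the effect expressed: 0.12 × 0.5/3 = 0.02 to 0.66 × 2/3 = 0.44 log10.
- Five users among 15, all on-phase starters: 5 × 0.5/15 = 0.17 to 5 × 2/15 = 0.67 log10.
- Five users among 15, three on and two off: a net 0.5/15 = 0.03 to 2/15 = 0.13 log10.

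The user counts are also illustrative, because the documents do not say how many subjects use these drugs on alternate months.

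**The case against.** Several points on the other side have weight.

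- **Attenuation.** Baseline lies exactly at the switch only when Day 1 is phase day 1. If it falls several days later and the antibiotic acts fast, little of the effect remains in the change. This stands, and it makes 0.17–0.67 log10 a worst case.
- **Direction.** The rule does not choose on or off, so starters of both kinds may occur and partly cancel. This also stands. What remains then is mainly extra noise and possible imbalance between small cohorts.
- **Dose comparison.** Section 15.4 compares the MTD with lower doses, and a phase effect common to all cohorts would drop out of that contrast. This is correct, but with cohorts of three an even spread of a few users cannot be relied on.
- **Consequence.** CFU is one of many safety measures and is only displayed, and the sputum markers are exploratory. DLTs are grade ≥3 infusion-related allergic toxicities within 24 hours, a definition into which antibiotic phase does not enter. The DMC reviews each cohort before the next, but no stated stopping rule uses CFU.
- **Existing data.** Section 9.1.1 already documents concomitant medications at all visits, individual-level summaries and patient profiles are planned, and section 15 says a detailed SAP is still to be written. Most of the raw material for the fix is therefore in place.

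A reader might infer from the calendar arithmetic that Baseline is always on the switch, so that any CFU or marker change in this trial is an antibiotic artefact in a known direction. The documents do not support that: Day 1 can be as late as phase day 6, the phase is unspecified, only alternate-month users are affected, and their number is not given.

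**Conclusion.** The point holds as a cheap improvement to the analysis. Following the rule exactly places Day 1 within the first 1 to 6 days of a phase (1 to 4 if Visit 5 is on Day 28), given phases of 28 to 31 days. In alternate-month users, the change from Baseline can then contain anything from a small part to nearly all of the antibiotic's on/off effect, and nothing in section 15 would reveal it. The worst-case shift for one user in a cohort of three is 0.17 to 0.67 log10 CFU. That figure rests on an assumed effect of 0.5 to 2 log10, fully expressed; the phase length, response half-lives and user counts are assumptions too.

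The issue is limited to interpreting CFU and the exploratory sputum markers. A reader might go further and doubt the MTD or the dose-escalation decisions. The documents give no ground for that, since neither the DLT definition nor any stated stopping rule uses these measures.

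Separately, the Day 30 end of the Visit 5 window contradicts the same-phase rule if a phase lasts 28 or 29 days.

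**What to change.** 1. For each alternate-month user, record the drug, on/off status and cycle day at Visits 2, 3 and 5.
2. In sections 15.3 and 15.4, and in the SAP when it is written, present CFU and sputum-marker changes for all subjects and again excluding alternate-month users.
3. Mark on-phase and off-phase starters in the individual profiles.
4. Reconcile the Visit 5 window in section 10.10 with the same-phase rule in section 7 and the synopsis. This review takes no position on when antibiotic treatment should be given.

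The cost is one CRF item and one repeat summary. The summary without alternate-month users will rest on fewer subjects and be less precise, so it should be read beside the full one and not in its place.

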7.1 Allowed

Except as noted in the prohibited medications section below or in the exclusion criteria described above, all usual CF medications and treatments are allowed. A stable therapeutic regimen (including physiotherapy) between screening and Visit 5 (Day 28) is the goal. Ongoing *chronic* treatment (> 4 weeks prior to screening) with Pulmozyme®, Cayston®, TOBI®, nebulized colistin, Kalydeco®, Orkambi®, high-dose ibuprofen, hypertonic saline, azithromycin, systemic or inhaled corticosteroids, short and long acting bronchodilators and airway clearance is allowed. Unless otherwise medically indicated, subjects not using these therapies should not be started on them from screening through Visit 5 (Day 28) and subjects that have been using them chronically should be encouraged to continue them through Visit 5 (Day 28). Limited use of over-the-counter anti-inflammatory drugs (acetaminophen, aspirin, ibuprofen, or naproxen) from screening through Visit 5 (Day 28) is acceptable.

7.2 Prohibited

- Intravenous antibiotics from 14 days prior to the screening visit through Visit 2 (Day 1)
- Newly prescribed oral or inhaled antibiotics prescribed for acute symptoms from 14 days prior to the screening visit through Visit 2 (Day 1)
- Systemic corticosteroids prescribed for an acute issue or for chronic therapy if the dose exceeds a prednisone equivalent of 10 mg every day or 20 mg on alternate days (maximum allowable dose for chronic systemic corticosteroids is 20 mg of prednisone or its equivalent over a two day period) from screening through Visit 5 (Day 28)
- Hydroxychloroquine from screening through Visit 5 (Day 28)
- Other immunosuppressants from screening through Visit 5 (Day 28)
- The use of an investigational agent within 4 weeks prior to Visit 1 (Day -42 to -10)

8 STUDY TREATMENTS

8.1 Method of Assigning Subjects to Treatment Groups

In this Phase I open-label study, there is no placebo group. All subjects will receive a single infusion of hMSCs. 15 eligible subjects will be recruited from the adult CF Center located at Rainbow Babies and

Children's Hospital and will receive a single dose of one of the following doses of hMSCs: 1×10^6 , 3×10^6 or 5×10^6 hMSCs/kg body weight. A traditional 3+3 design will be utilized (Figure 4). If a maximum tolerated dose (MTD) is identified among the 3 doses, the next 3 subjects enrolled will receive the identified MTD. If there are no DLTs or one DLT, the next 3 subjects enrolled will receive same dose. If there are two or more DLTs, the next lower dose will be used as the MTD for the final 3 enrolled study subjects.

[figure not shown]

Figure 4. Study design for determining dose-limiting toxicity

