8.3.3 Dosage/Dosage Regimen

The first cohort of 3 subjects enrolled will receive a single infusion of 1×10^6 hMSCs/kg body weight. The second cohort of three subjects enrolled will receive a single infusion of 3×10^6 hMSCs/kg, and the third cohort of three subjects enrolled will receive a single infusion of 5×10^6 hMSCs/kg. The first subject in the subsequent cohort will not be enrolled until the last subject in the preceding cohort has completed Visit 5 (Day 28). There will be a minimum of 1 week between the dosing of each study subject in the first three cohorts. The final six subjects will receive a single infusion of 5×10^6 hMSCs/kg if that dose was well tolerated. If the highest dose was not well tolerated, then the final six subjects will receive the maximum tolerated dose (either 1×10^6 or 3×10^6 hMSCs/kg body weight).

Table 1: hMSC dose cohorts

Cohort 1	1×10^6 hMSCs/kg	3 subjects
----------	--------------------------	------------

Cohort 2	3×10^6 hMSCs/kg	3 subjects
Cohort 3	5×10^6 hMSCs/kg	3 subjects
Cohort 4	MTD	6 subjects

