14 DATA SAFETY MONITORING

The Cystic Fibrosis Foundation Data Safety Monitoring Board (DSMB) will establish a Data Monitoring Committee (DMC) to review data relating to safety and efficacy, to conduct and review interim analyses, and to ensure the continued scientific validity and merit of the study, according to the Cystic Fibrosis Foundation Data Safety Monitoring Board Operations Manual and a DMC Charter to be established for this protocol. There will be 3 interim review(s) conducted by the DMC for the purpose of monitoring study conduct and assessing subject safety. Enrollment for subsequent cohorts will not begin until after the DMC reviews the data for the current cohort and approves proceeding to the next cohort. Further details regarding the timing and content of the interim reviews is included in the statistical section below.

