15.6 Sample Size

This is a single center Phase I study. Enrollment of 15 subjects will be feasible and allow us to ascertain if there are any clinically meaningful infusion-related adverse effects.

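### Section 8.1 names a traditional 3+3, but 8.3.3 and Table 1 fix the cohorts at 3, 3, 3 and 6 with no step for one DLT in three, so the stated total of 15 is the count when no level expands

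*Combined protocol and SAP*

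**What the plan says.** Section 8.1 names the design: "A traditional 3+3 design will be utilized (Figure 4". The synopsis also refers to a 3+3. Section 8.1 gives the total as well: "15 eligible subjects will be recruited from the adult CF Center located at Rainbow Babies and" the affiliated children's hospital.

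The only sentences in the readable text that turn on a count of DLTs are in 8.1, directly after the sentence on an identified MTD. With zero or one DLT, the next three subjects stay at the same dose. With two or more, the next lower dose becomes the MTD for the last three.

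Section 8.3.3 gives fixed cohorts:
- "The first cohort of 3 subjects enrolled will receive a single infusion of" 1 × 10⁶ hMSCs/kg.
- "The second cohort of three subjects enrolled will receive a single infusion of" 3 × 10⁶ hMSCs/kg.
- "the third cohort of three subjects enrolled will receive a single infusion of" 5 × 10⁶ hMSCs/kg.
- A final six receive the top dose if it was well tolerated. Otherwise: "If the highest dose was not well tolerated, then the final six subjects will receive the maximum tolerated dose".

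Table 1 repeats 3, 3, 3 and 6. The conditions written in 8.3.3 for opening a cohort are that the last subject of the previous cohort has completed Visit 5 and that dosings are at least a week apart.

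Section 14 adds that each later cohort opens only after the DMC has reviewed the current one and approved. It also says: "There will be 3 interim review(s) conducted by the DMC for the purpose of monitoring study conduct and assessing subject safety". For details it points to the statistical section, where 15.5 says only that no interim statistical analysis is planned.

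Section 15.6 supports the total on feasibility: "Enrollment of 15 subjects will be feasible and allow us to ascertain if there are any clinically meaningful infusion-related adverse effects". Fifteen is given without a range there, in the synopsis, and in 4.1, 5.2, 6.1 and 8.1.

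**The concern.** In a traditional 3+3, one DLT among three subjects leads to three more at the same level before any escalation. Section 8.3.3 and Table 1 have no such step and no room for it in the counts. Taken at their word, the two sections give different next steps after 1/3 at level 1 or 2: three more subjects at that level, or on to the next cohort.

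Section 15.3 makes identifying the MTD among the three doses the primary endpoint, so the cohort rule is the procedure that produces the primary result. It also decides who is exposed to the next dose, how many subjects are treated, and how large the final group is. That group provides most of the safety and biomarker data at the chosen dose.

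**Working it through.** **1. The plan's own figure.** Table 1: 3 + 3 + 3 + 6 = 15. The stated total reproduces, and it contains no expansion.

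**2. Can the DLT sentences in 8.1 serve as the missing rule?**
- Read as the escalation rule, zero or one DLT keeps the next three at the same dose and two or more moves down. Nothing leads upward.
- Read as the final-phase rule, which their position after the MTD sentence suggests, they split the last six into 3 + 3 and keep the total at 15. Levels 1 and 2 then have no DLT rule.

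**3. Totals under a standard 3+3.** Rule used: 0/3, escalate; 1/3, add three; 1/6, escalate; two or more DLTs, level exceeded and the level below is the MTD; then six more at the MTD. There are 22 paths, of which 18 contain a 1/3 result:

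| Final N | Paths with a 1/3 result |
|---|---|
| 6 | 1 (level 1 expands and is exceeded) |
| 15 | 2 |
| 18 | 7 |
| 21 | 6 |
| 24 | 2 |

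The two paths that stay at 15 are:
- 0/3 at level 1; 1/3 then exceeded at level 2; six at level 1: 3 + 6 + 6.
- 1/6 at level 1; at least 2/3 at level 2; six at level 1: 6 + 3 + 6.

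Where escalation reaches the top dose and k levels expand, N = 15 + 3k, that is 18, 21 or 24. Holding 15 in that case leaves 15 − 9 − 3 = 3 for the final group after one expansion and none after two. Without a 1/3 result, N can also be 3 or 12.

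If the three expansion subjects at the MTD count towards the six, 4 of the 18 paths give 15 and the maximum is 21.

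**4. Probabilities.** The documents give no DLT rate, so p is assumed, the same at every level. For one level, with p = 0.05:
- 0/3: a = 0.95³ = 0.8574
- 1/3 then 0/3: b = 3(0.05)(0.95²) × 0.8574 = 0.1354 × 0.8574 = 0.1161
- 1/3 then exceeded: c = 0.1354 − 0.1161 = 0.0193
- at least 2/3: d = 0.0073

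Then:
- P(N = 15) = a³ + a²d + ac + bd = 0.6302 + 0.0053 + 0.0166 + 0.0008 = 0.653
- P(N < 15) = d + c + ad = 0.0073 + 0.0193 + 0.0062 = 0.033
- P(N > 15) = 1 − 0.653 − 0.033 = 0.314
- P(some level reached shows 1/3) = 1 − (a³ + a²d + ad + d) = 1 − 0.649 = 0.351

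Repeating this over a range of assumed rates:

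| Assumed DLT rate | P(N > 15), six always added | P(N > 15), expansion subjects at MTD count |
|---|---|---|
| 1% | 8% | 6% |
| 2% | 16% | 11% |
| 5% | 31% | 23% |
| 10% | 43% | 32% |

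The chance that some level reached shows 1/3 is 35% at a 5% rate and 55% at 10%. At those two rates, given a 1/3 result, N is still 15 in 5% and 10% of trials if six are always added, and in 30% and 29% if expansion subjects count.

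**The case against.** **Figure 4 may contain the branches.** Section 8.1 points to it for the 3+3, and it is not reproduced in the text reviewed. This stands: one cannot say that the plan lacks the rule. Even so, branches in a figure would leave Table 1's fixed counts and the unqualified 15 at odds with it.

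**The site does not escalate on its own.** A reader of 8.3.3 alone might infer that the next cohort opens whatever the DLT count. Section 14 rules that out by requiring DMC approval. What remains is that the readable text gives no DLT criterion for that approval.

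**Fifteen can survive an expansion.** A reader might infer that 15 is impossible after any 1/3 result, or that one expansion always needs 18 and two always need 21. Neither is true. Two paths with a 1/3 result still end at 15, one ends at 6, and two expansions can give 6 + 6 + 6 = 18. The 3 + 3 reading of 8.1 also allows expansion subjects at the MTD to count towards the final six.

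**DLTs may be rare.** As applied in 5.1, a DLT is a grade 3 or higher infusion-related allergic toxicity within 24 hours, and the trials summarised in 1.3.2 and 1.3.4 report no infusion-related toxicities. That favours the lower rows of assumed rates, where the chance of exceeding 15 is 6% to 16%. It lowers the likelihood of the conflict arising but does not settle what happens if it does.

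**Fifteen is naturally read as a planning number.** Section 6.1 already allows replacement of subjects who withdraw before Visit 5. That is a fair reading, but no section states it for expansion.

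The count of three DMC reviews is secondary: it fits three unexpanded cohorts, but could also mean one review per level after any expansion.

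**Conclusion.** The concern holds in this form: the named design and the dosing section disagree on what follows one DLT in three, and the readable text does not resolve it. Fifteen is the total when no level expands, not a total that the named design guarantees. If a final six is always added, N runs from 3 to 24, and a 1/3 result usually takes it to 18–24.

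The chance of exceeding 15 is about 8% to 43% across assumed DLT rates of 1% to 10%, or about 6% to 32% if expansion subjects at the MTD count towards the six. These figures rest on assumed rates, equal at every level, and on the standard 3+3 rule set out above.

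The likelihood may be modest, but the gap concerns the rule that yields the primary endpoint and governs exposure to higher doses, so it should be corrected. Which rule is right is not judged here.

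**What to change.** - Reconcile 8.1, Figure 4, 8.3.3, Table 1, section 14 and 15.6 to one cohort rule chosen by the sponsor, so that a 1/3 result has a single stated consequence at every level.
- In 15.6 and wherever 15 appears, describe it as the total when no level expands and give the minimum and maximum N. Alternatively, state that the final group is reduced to hold 15.
- State whether expansion subjects treated at the MTD count towards the final six.
- Align the number and timing of DMC reviews in section 14 with the chosen rule, and supply the details that section 14 says are in the statistical section.

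The cost is protocol wording. No subjects are added when no level expands. The downside is that the stated total becomes a range, or the final cohort may be smaller than six.
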